1.2 Secondary Objectives

- To determine whether the SPR after receiving 2 vaccinations of Sci-B-VacTM, evaluated at 4 weeks and 20 weeks after receiving the second vaccination (just prior to receiving the third vaccination), is non-inferior to the SPR 4 weeks after receiving the third vaccination with Engerix-B®
- To compare the safety and reactogenicity of Sci-B-VacTM and Engerix-B®.

1.3 Exploratory Objectives

- To compare the geometric mean concentration (GMC) of anti-HBs 4 weeks after receiving the first vaccination, the second vaccination and the third vaccination, 20 weeks after receiving the second vaccination (just prior to receiving the third vaccination), and 24 weeks after receiving the third vaccination, of Sci-B-VacTM or Engerix-B®.
- To compare the SPR observed 4 weeks after receiving the first vaccination and second vaccination, 20 weeks after receiving the second vaccination (just prior to receiving the third vaccination), and 24 weeks after receiving the third vaccination, of Sci-B-VacTM or Engerix-B® on Study Days 28, 56, 168 and 336.
- To compare the proportion of subjects who achieve anti-HBs levels ≥ 100 mIU/mL, as a measure of an especially robust immune response, 4 weeks after each vaccination with either Sci-B-VacTM or Engerix-B®, on Study Days 28, 56, and 196, and on Study Days 168 and 336.
- To compare the rate of non-response 4 weeks after receiving the third vaccination with Sci-B-Vac[™] or Engerix-B®.
- To assess the antibody responses against Pre-S1 and Pre-S2 at baseline, 4 weeks after each injection with Sci-B-VacTM or Engerix-B® and on Study Days 168 and 336.
- To compare SPR, GMC and rate of non-response in subgroups of interest (e.g. BMI>30) 4 weeks after receiving the third vaccination with Sci-B-VacTM or Engerix-B®.
- To compare clinical laboratory parameters relative to baseline 1 week after each vaccination with Sci-B-VacTMor Engerix-B® in a subset of subjects (at least 10% of the total number of subjects enrolled to the trial).
- To compare the boost, relative to baseline, of cell-mediated immune response against HBs, 1 week after receiving each vaccination with either Sci-B-VacTM or Engerix-B® (in a small subset of subjects recruited to an optional sub study at select sites (~50-75 subjects/treatment arm)).

Statistical Analysis Plan

[figure not shown]
2. STUDY DESIGN

This is a double-blind randomized controlled trial designed to establish the non-inferiority of Sci-B-VacTM compared to Engerix-B® in adults ≥18 years old. Study subjects will be randomized 1:1 via a web-based system to receive either a total of 3 injections of Sci-B-VacTM or 3 injections of Engerix-B® intra-muscularly (IM) (one injection on Study Day 0, one injection at 4 weeks (Study Day 28) and one injection at 24 weeks (Study Day 168)), and followed for 24 weeks after receiving the third vaccination.

Randomization will be stratified by study center, and age (18-44 years, 45-64 years and \geq 65 years). The study subjects, the study center staff performing outcome measurement, and the sponsor will be blinded to vaccine allocation. Study vaccines will be administered by qualified unblinded study center staff.

The scheme of the study design is as Figure 1. For further details please refer to section 3.1 of the Protocol.

Figure 1: Schematic of Study Design

Statistical Analysis Plan

3. STUDY POPULATION

The study population will consist of approximately 1,564 subjects, age \geq 18 years old, in up to 30 study centers in Europe, Canada, and the U.S individuals of any gender, race and ethnic groups meeting all the inclusion criteria and none of the exclusion criteria.

Inclusion criteria

Subjects must meet all the following criteria:

- 1. Any gender
- 2. Age ≥ 18 years
- 3. In stable health as determined by a physical examination and laboratory tests values. Common chronic conditions such as, but not limited to, type 2 diabetes, high blood pressure, COPD and asthma will be accepted if the condition is well controlled, as determined by the investigator, and not meeting the exclusion criteria. For subjects > 65 years old, Frailty Index ≤3 (see protocol Appendix 1).
- 4. If female: a) either is not of childbearing potential, defined as postmenopausal for at least 1 year or surgically sterile (bilateral tubal ligation, bilateral oophorectomy or hysterectomy), OR b) is of childbearing potential and must agree to use an adequate birth control method during the screening period and until the end of her participation in the study (effective birth control includes: 1) hormonal (implant, oral, vaginal, transdermal) contraceptives; 2) diaphragm with spermicide, condom (with or without spermicide); 3) intra-uterine devices; and 4) vasectomy of male partner; 5) abstinence from penile-vaginal intercourse (if the preferred and usual lifestyle of the subject)).
- 5. Able and willing to give informed consent

Main Exclusion criteria

Main exclusion criteria are listed below, for the complete list of exclusion criteria please refer to section 4.1.2 of the Protocol. Participants meeting any of the exclusion criteria will be excluded.

- 1. Previous vaccination with any HBV vaccine (licensed or experimental).
- 2. Treatment by immunosuppressant within 30 days of enrollment including but not limited to corticosteroids at a dose that is higher than an oral or injected physiological dose, or a prednisolone-equivalent dose > 20 mg/day (Inhaled and topical steroids are allowed)
- 3. Known history of immunological function impairment, including but not limited to: a) autoimmune diseases (e.g., multiple sclerosis, type 1 diabetes, myasthenia gravis, Crohn disease and other inflammatory bowel diseases, celiac disease, systemic lupus erythematosus, scleroderma, including

Statistical Analysis Plan

diffuse systemic form and CREST syndrome, systemic sclerosis, dermatomyositis polymyositis, rheumatoid arthritis, juvenile idiopathic arthritis, autoimmune thyroiditis -including Hashimoto thyroiditis, Grave's or Basedow's disease, immune thrombocytopenic purpura, autoimmune hemolytic anemia, autoimmune hepatitis, psoriasis, vitiligo, vasculitis, Guillain-Barré syndrome, Addison's disease, Bell's palsy and alopecia areata) OR

- b) secondary immunodeficiency disorders (e.g. resulting from HIV/AIDS (Acquired Immunodeficiency Syndrome caused by Human Immunodeficiency Virus infection), solid organ transplant, splenectomy...) OR
- c) primary immunodeficiency disorders (e.g. common variable immune deficiency (CVID), Defective phagocytic cell function and neutropenia syndromes, complement deficiency...)
- 4. Pregnancy or breastfeeding
- 5. Immunization with attenuated vaccines (e.g. MMR) within 4 weeks prior to enrollment.
- 6. Immunization with inactivated vaccines (e.g. influenza) within 2 week prior to enrollment.

4. STATISTICAL BASIS FOR SAMPLE SIZE

The overall sample size for the study is driven by the superiority co-primary analysis in study subjects ≥ 45 years old. Assuming an SPR of 0.81 for Engerix-B® and 0.96 for Sci-B-VacTM, a minimum of 540 subjects (270 per treatment group) provides 90% power to demonstrate superiority of SPR, assuming a 5% margin with a two-sided type 1 error of 0.05, i.e., to rule out a <5% difference in SPR based on the lower limit of the two-sided 95% confidence interval. Based on a targeted enrollment of 80% of study subjects age ≥ 45 years old, an additional 180 (20%) 18-44 years old study subjects would be required, for a total of at least 680 subjects in the full study. A sample size of 680 would provide ≥ 90% power to demonstrate non-inferiority with a 5% margin if the Sci-B-VacTM SPR is as low as 0.88, with the same SPR for Engerix-B® (0.81), and the two-sided alpha is 0.05. A 5% margin of non-inferiority is justified by the > 90% SPR of Engerix-B® in young adults. In older adults, a 5% margin of superiority represents a clinically meaningful improvement at both the individual level and from a public health perspective, given the reduced immunogenicity of Engerix-B® in this population.

Given the desire to have robust immunogenicity estimates of SPR in the adult population following a three-dose regimen of Sci-B-VacTM and to guard against a better than expected SPR for Engerix-B® (up to 84% in subjects \geq 45 years old), a total of 1,564 subjects will be enrolled to the trial. There will be targeted enrollment, with 80% (\sim n=1252) of the study population being \geq 45 years old and 20% (\sim n=312) being 18-44 years old. This sample size will provide >90% power to establish the superiority of Sci-B-

Statistical Analysis Plan

VacTM over Engerix-B® in older adults (\geq 45 years old) and non-inferiority in adults \geq 18 years of age,

given the above statistical parameters.

Given the desire to have good representation across the spectrum of older adults, the targeted enrollment of adults \geq 45 years of age (80%) will be divided equally between the 45-64 years old and \geq 65 years old

strata.

Targeted enrollment by age strata will be as follows:

Age 18-44 years (20%): 312 (~ 156 per arm)

Age 45-64 years (40%): 626 (~313 per arm)

Age \geq 65 years (40%): 626 (~313 per arm)

Enrollment within each stratum will be stopped once the target has been met.

5. RANDOMIZATION

This is a double blind 2-arm study. A statistician who is not involved in the clinical aspects of the study will generate a permuted blocked randomization list for each site and inside each site for each of the 3 following strata: 18-44 years, 45-64 years and \geq 65 years old at the date of enrolment. Randomization will be via a web-based IWRS. The site pharmacy and/or unblinded study center staff will receive a notification of the randomization and the treatment allocation for the subject, which should be filed in a locked area/ computer folder not accessed by blinded study center staff. The IWRS will track and supply

appropriate medication to the study subjects.

Randomization within an age stratum will stop after the target sample size has been reached.

5.1 **Definition of Vaccination/Randomization Errors**

The list below provides some examples of potential errors that may occur during vaccination:

Subjects vaccinated with a vaccine different from the one assigned at randomization.

Subjects vaccinated with the correct vaccine but containing a lower volume.

Please see section 6 of this document for a complete guidance on how vaccination/randomization errors

are handled in the statistical analysis.

Statistical Analysis Plan

6. STATISTICAL ANALYSIS CONVENTIONS

6.1 Analysis Variables

Baseline characteristics, medical history, vaccination, immunogenicity (measurement of anti-HBs), concomitant medication, adverse events (AEs) and other safety assessments will be assessed according to the schedule of events listed as following:

	Screening	. V1	Phone Safety Follow-up	٧2	Phone Safety Follow-up	V3 (i)	٧4	Phone Safety Follow-up	VS (j)	V6 End of Study Visit
Timelines (days)	-28	0		28	_	56	168		196	336(a)
Range (days)	-28 to 0		V1 + 5-9	-3/+7	V2 + 5-9	-3/+7	+/-7	V4 + 5-9	+/-7	+/-14
Screening										
Informed Consent	Χ									
Inclusion & Exclusion Criteria	Χ									
Physical Examination (b)	Χ	Χ		Х		Х	Χ		Х	Χ
Medical History	Χ									
Height and weight	Χ									
Medications	Χ									
HBV serology	Χ									
HIV and HCV serology	Χ									
Urine Pregnancy test	Χ	х		х			Х			
Blood tests: CBC, liver and renal function, HbA1C if indicated	Х									
Urinalysis	Х									
Randomization		Х								
Vaccination		Χ		Х			Х			
Immunogenicity		\ \ \ \ \		24()		.,				.,
Anti-HBs		X(c)		X(c)		X	X(c)		X	X
Anti pre-S1, anti pre-S2		X(c)		X(c)		Х	X(c)		Χ	Х
Safety Assessments Vital signs	Х	X(d)		X(d)			X(d)			
Vital signs Subject instructed to complete diary	^	X(u)	Х	X(u)	Х		X(u)	Х		
Recording Local & Systemic Reactions		X	X(e)	X	X(e)		X	X(e)		
Recording Concomitant Medications	Х	X	X(e)	X	X	Х	X	X(e)	Х	Х
Unsolicited AEs	X	X	X(g)	X(g)	X(g)	X(f)	X(g)	X(g)	X(g)	X(f)
SAEs, medically significant event, NOCI (h)		^	^\8/	^(8)		tinuous	^(8)	^(8/	^(g )	^(1)
Sub-Studies (only at select sites)			A1*		A2*	itiiladas		A3*		
Serum chemistry, Hematology		X(c)	x(k)		x(k)			x(k)		
Cell-mediated immunity		X(c)	x(k)		x(k)			x(k)		

Statistical Analysis Plan

- (a) Or earlier in case of withdrawal
- (b) Full physicals to be done at screening or pre-vaccination at Day 0. Historydirected physicals can be completed at subsequent visits.
- (c) Blood sample at V1, V2 & V4 will be taken before vaccination
- (d) Vital signs will be recorded before and 30 minutes after each vaccination.
- (e) Subjects will be instructed to record solicited and unsolicited AES. There will be a telephone call 1 week after each vaccination to inquire about reaction to vaccine. If there is a reaction the subject may be asked to come for a supplemental visit (not represented in this table) to assess severity at the discretion of the investigator. Follow-up until resolution.
- (f) Only AEs requiring medical attention
- (g) All AEs
- (h) NOCI: new onset of chronic illness
- (i) V3 should be scheduled at least 3 weeks after V2
- (j) V5 should be scheduled at least 3 weeks after V4
- (k) Blood sample collected 7 days (-3/+7 days) after vaccination

* Additional visits (A1, A2 and A3) required for study subjects at select sites participating in the clinical laboratory sub-study. A small subset of subjects participating in the clinical laboratory sub-study will be eligible to participate in an optional sub-study on cell-mediated immunity.

6.1.1 Derived and Computed Variables

Demographics

Body Mass Index (BMI, kg/m²) will be calculated using the following formula:

$$BMI = Weight (kg) / Height^2 (m^2)$$

Immunogenicity

Values below the lower limit of quantification (recorded as "< LQ") will be set to half that limit (LQ/2).

Values above the initial upper limit of quantification (recorded as ">UQ") will be set to that upper limit (UQ). Samples which initially report ">UQ" will be further manually diluted and tested. These manually diluted and tested sample values will be reported in the listings only.

Titer greater or equal to a given threshold is defined as binary variable for non-missing values as:

- = 1, if the titer is superior or equal to the given threshold
- = 0, otherwise

Seroprotection is defined as binary variable for non-missing values as:

- = 1, if anti-HBs levels \geq 10mIU/mL in serum
- = 0, otherwise

Seroprotection rate (SPR) is the percentage (%) of subjects achieving seroprotection.

Statistical Analysis Plan

An initial result of >= 5.0 and <12.0 mIU/mL ("Indeterminate") required duplicate retest per Laboratory Procedure Manual. In the statistical analysis, if the anti-HBs serology result is initially indeterminate, then the average of initial and repeat results will be calculated. Seroprotection will be determined as follows: if the average of initial and repeat results is \geq 10 mIU/mL, then it will be considered seroprotected. If it is less than 10 mIU/mL, then it will be considered not seroprotected.

Geometric Mean Concentration

The GMC will be calculated using the following formula:

$$10^{\left\{\sum_{i=1}^{n}\log_{10}\left(t_{i}\right)\atop n\right\}}$$

where t_1, t_2, K , t_n are n observed immunogenicity titers/concentrations.

Solicited Adverse Events

Reactions at the site of injection (redness/erythema, pain, tenderness, swelling/edema, pruritus), systemic reactions (nausea/vomiting, diarrhea, headache, fatigue, myalgia) and vital signs abnormalities (fever, tachycardia, bradycardia, hypertensions, hypotension, changes in respiratory rate).

Unsolicited Adverse Events

All adverse events will be characterized according to the date of occurrence related to the vaccination phase as follows:

- Emergence before vaccination phase: start date before the first date of injection of study vaccine.
- **Emergence during vaccination phase**: start date on or after the first date of injection of study vaccine or, adverse event increase in severity including to "serious" adverse event.

If an adverse event start date is equal to the first date of vaccination injection, missing or unknown, the adverse event will be considered as emergent.

When start and/or end dates of an adverse event are only partially known, adverse events will be categorized as emergent before, during (or after) vaccination phase using the following rules:

• If the partial end date is before (<) the first study vaccination (i.e., year or year & month is/are before the first study vaccination year or year & month) then the adverse event is emergent before vaccination phase.

Statistical Analysis Plan

If the partial start date is equal or after (≥) the first study vaccination (i.e., year or year & month is/are after or the same as the first study injection year or year & month) then the adverse event is emergent during vaccination phase.

The **maximum event severity** is the greatest severity associated with a preferred term for a reported adverse event according to the following order: Mild < Moderate < Severe < Potentially life threatening. Unknown/ Missing severity is considered as potentially life threatening.

Multiple AEs with the same PT for the same subject are counted only once.

Vaccination-related Adverse Events are those for which the cause has been evaluated by the investigator, and recorded either as very likely/certain, possibly related, probably related or unknown/missing.

Pre-Study, Concomitant and Post-Study Medications

A **pre-study medication** is a medication used only before the first study vaccination (i.e. medication end date < first study vaccination date).

A **post-study medication** is a medication used only after study termination (i.e. medication start date > study termination date). This will not be collected in the clinical database and will not be reported in the CSR.

All other medications are **concomitant**.

When start and/or end dates of a medication intake are missing, the medication is considered as concomitant with the study vaccination schedule.

If the first study vaccination date is missing then the medication is considered as concomitant with the study vaccination schedule, provided that the study vaccine was administered to the subject.

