3.2 Primary endpoint

• Seroprotection rate 4 weeks after receiving third vaccination with either Sci-B-Vac[™] or Engerix-B®, on Study Day 196. Seroprotection is defined as anti-HBs levels ≥ 10 mIU/mL in serum. Seroprotection rate is the percentage (%) of subjects achieving seroprotection. A validated quantitative antibody test will be used to measure anti-HBs levels in serum.

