9.7 Exploratory Immunogenicity Endpoints

Analysis of all exploratory immunogenicity endpoints will be based on the PPS, unless otherwise indicated. Geometric Mean Concentration (GMC)

All statistical analyses will be performed on the logarithmically (base 10) transformed values. Individual titers below the detection limit will be set to half the limit.

Adjusted estimates of GMCs and their associated 95% CIs at day 28, day 56, day 168, day 196 and day 336 will each be determined using an analysis of covariance (ANCOVA) model with factors for treatment, age group, and a covariate for the log transformed pre-vaccination (baseline) titer. Antibody GMCs, associated standard errors, two-sided 95% CIs and median, minimum, and maximum titer values will be determined and presented by treatment group. The median, minimum, and maximum values will be reported on the actual titer values, rather than the log scale. The difference in GMCs between the two treatment groups, and associated two-sided 95% CIs will also be presented. For immunogenicity data, it may be reasonable to consider missing immunogenicity values as missing completely at random (MCAR), i.e., not informative. Therefore, this analysis will comprise a complete case analysis only, without introducing any bias. Imputation methods will not be used.

The above analyses will be conducted and reported for all subjects age \geq 18 years old and for subjects age \geq 45 years old. Analyses of GMC in both age cohorts will also be reported by sub-group using the subgroups identified in section 9.3.7. Sub-group analyses will include additional factors in the model, a factor for the sub-group of interest and the interaction between the sub-group and treatment.

Binary Data

All binary data will be summarized using frequency counts and percentages, by time point. Data from all centers will be pooled for these analyses. The difference in adjusted proportions and two-sided 95% CIs, calculated using the Miettnen and Nurminen method, will be reported. Additional sensitivity analyses will be conducted using a Log Linear model, to adjust for age group. Factors for treatment and age group will be included in the model. For immunogenicity data, it may be reasonable to consider missing immunogenicity values as missing completely at random (MCAR), i.e., not informative. Therefore, the analysis will comprise a complete case analysis only without introducing any bias. Imputation methods will not be used.

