6.3.13 Immunogenicity

The co-primary analyses of the immunogenicity data will be based on the PPS and FAS. Sensitivity analyses using the same approach will be conducted using the ITT. These analyses will be reported both with and without patients in the FAS or ITT who are seropositive at baseline.

Immunogenicity (measurement of anti-HBs titer) data will be listed by subject including actual sampling times relative to dosing. Serum concentrations will be summarized by treatment group. The following descriptive statistics will be presented for serum concentrations obtained at each nominal time point: n, geometric mean, geometric SD, median, minimum and maximum values.

Individual serum concentration versus actual times will be plotted by treatment group for anti-HBs antibody in linear and semi-logarithmic scale. The geometric mean serum concentrations with

Statistical Analysis Plan

corresponding 95% confidence intervals versus nominal times will also be presented. The bar plot of SPR by treatment on Days 28, 56 and 196 will also be produced based on PPS for all age groups and for age >= 45 years old. All treatment groups will be overlaid on the same plot.

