6.3.13.4 Exploratory Objective Analyses

Analysis of all exploratory immunogenicity endpoints will be based on the PPS, unless otherwise indicated. Exploratory efficacy endpoints will be summarized and analyzed without adjustment for multiple comparisons.

Geometric mean concentration (GMC)

All statistical analyses will be performed on the logarithmically (base 10) transformed values.

Statistical Analysis Plan

Adjusted estimates of GMCs and their associated 95% CIs at Day 28, Day 56, Day 168, Day 196 and Day 336 will each be determined using an analysis of covariance (ANCOVA) model with factors for treatment, age group, and a covariate for the log transformed pre-vaccination (baseline) titer. Antibody GMCs, associated standard errors, two-sided 95% CIs and median, minimum, and maximum titer values will be determined and presented by treatment group. The median, minimum, and maximum values will be reported on the actual titer values, rather than the log scale. The difference in GMCs between the two treatment groups, and associated two-sided 95% CIs will also be presented. Imputation methods will not be used.

The above analyses will be conducted and reported for all subjects age \geq 18 years old and for subjects age \geq 45 years old. Analyses of GMC in both age cohorts will also be reported by sub-group using the sub-groups identified in Section 6.2.7. Sub-group analyses will include additional factors in the model, a factor for the sub-group of interest and the interaction between the sub-group and treatment.

Sample SAS code for ANCOVA model:

```
PROC MIXED;
CLASS treatment agegrp;
MODEL log(var) = treatment agegrp log(baseline of var);

/* var = anti-HB titer GMC */
LSMEANS treatment / DIFF CL ALPHA=0.05;
ODS OUTPUT LSMEANS=ls_means Diffs=diff;

QUIT;
RUN;
```

Sample SAS code for ANCOVA model for sub-group analyses:

```
PROC MIXED;
CLASS treatment agegrp;
MODEL log(var) = treatment agegrp log(baseline of var) subgroup subgroup*treatment;
LSMEANS treatment / DIFF CL ALPHA=0.05;
ODS OUTPUT LSMEANS=ls_means Diffs=diff;
QUIT;
RUN;
```

where var represent the anti-HBs titer, treatment represents treatment group, agegrp represents age group (18 - 44 years, 45 - 64 years, >=65 years) and subgroup represents subgroup defined in Section 6.2.7.

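### Anti-HBs results above the upper quantification limit are analysed at that limit although diluted re-test values exist, which understates the GMCs of any arm that has such results

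*SAP*

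**What the plan says.** SAP 6.1.1 (Immunogenicity) states that a result above the initial UQ "will be set to that upper limit". The same samples are then manually diluted and tested again, but: "These manually diluted and tested sample values will be reported in the listings only".

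The affected variable feeds two sets of results:
- SAP 6.3.13 summarises serum concentrations at each nominal time point by "geometric mean, geometric SD, median, minimum and maximum values".
- SAP 6.3.13.4 calls for "Adjusted estimates of GMCs and their associated 95% CIs at Day 28, Day 56, Day 168, Day 196 and Day 336" from an ANCOVA on log10 values, and for the between-arm difference with its interval. These are reported for adults aged 18 and over and 45 and over, and by sub-group.

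Neither section brings the diluted values back, names a censored-data method, or plans a sensitivity analysis for values above UQ. Protocol 9.7 has a substitution rule for the lower end only: "Individual titers below the detection limit will be set to half the limit". The upper cap appears only in the SAP. Neither document gives a numerical UQ.

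**The concern.** GMC comparison is an exploratory objective at five visits, and the study rationale (Protocol 1.4) is that Sci-B-Vac gives generally higher antibody responses. A cap acts on the high end of the distribution, where such a difference would show. No subject is dropped, but each value above UQ enters as if it were exactly UQ, although a measured value exists.

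Three things follow for an arm with values above UQ:
- its GMC is understated;
- its SD is usually narrowed, so the interval is too tight around a displaced estimate;
- its maximum is UQ rather than a measured concentration.

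If the arms have similar spread and one has higher titres, the ratio is pulled towards 1. With clearly unequal spread it can move the other way. Medians change only if more than half of an arm exceeds UQ.

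**Working it through.** **Direction.** For any titre t above UQ, log10(min(t, UQ)) is below log10(t). The GMC formula in SAP 6.1.1 averages these logs, so one such value is enough to lower the unadjusted GMC. Example: 5, 50, 500, 5,000 and 50,000 have a GMC of 500; with UQ = 1,000 substituted it is 165.7. For the adjusted GMCs the same direction is expected. It appeared in every simulated case of a treatment-plus-age-group model with 156/313/313 per arm.

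**Size.** The plan has no GMC, SD or UQ figure to reproduce, so this is an illustration for Day 196 only.

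*From the documents:* SAP section 4, "Assuming an SPR of 0.81 for Engerix-B" and 0.96 for Sci-B-Vac; seroprotection threshold 10 mIU/mL.

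*Assumed:* normal log10 titres; equal SDs s of 0.6, 0.8 or 1.0; UQ of 1,000, 2,500 or 10,000 mIU/mL; 750 per arm.

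*Formulas,* with u = log10 UQ and a = (u − μ)/s:
- μ = 1 + s·z(SPR), so that P(titre ≥ 10) equals the SPR
- capped mean = μΦ(a) − sφ(a) + u(1 − Φ(a))
- capped second moment = (μ² + s²)Φ(a) − s(μ + u)φ(a) + u²(1 − Φ(a)), which gives the capped SD
- SE of the log10 difference = √((s₁² + s₂²)/750), using the capped SDs

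*One case in full (s = 0.8, UQ = 1,000):*
- Engerix-B: μ = 1 + 0.8 × 0.8779 = 1.7023 (GMC 50.4); a = 1.6221; capped mean = 1.7023 × 0.9476 − 0.8 × 0.1070 + 3 × 0.0524 = 1.6847 (GMC 48.4, 4.0% low).
- Sci-B-Vac: μ = 1 + 0.8 × 1.7507 = 2.4005 (GMC 251.5); a = 0.7493; capped mean = 2.4005 × 0.7732 − 0.8 × 0.3013 + 3 × 0.2268 = 2.2955 (GMC 197.5, 21.5% low).
- Ratio: 10^(2.4005 − 1.7023) = 4.99 uncapped; 10^(2.2955 − 1.6847) = 4.08 capped.
- Capped SDs 0.764 and 0.649; SE = √((0.5837 + 0.4212)/750) = 0.0366; 95% CI 3.46 to 4.81, which excludes 4.99.

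*GMC ratio, Sci-B-Vac to Engerix-B (95% CI):*

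| SD | Uncapped | UQ 10,000 | UQ 2,500 | UQ 1,000 |
|---|---|---|---|---|
| 0.6 | 3.34 (2.90–3.84) | 3.34 (2.90–3.84) | 3.32 (2.89–3.82) | 3.24 (2.83–3.71) |
| 0.8 | 4.99 (4.14–6.01) | 4.92 (4.09–5.92) | 4.60 (3.85–5.48) | 4.08 (3.46–4.81) |
| 1.0 | 7.46 (5.91–9.42) | 6.73 (5.40–8.40) | 5.56 (4.54–6.80) | 4.49 (3.73–5.39) |

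In three of the nine capped cases the interval excludes the uncapped ratio: SD 0.8 with UQ 1,000, and SD 1.0 with UQ 1,000 or 2,500.

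*Share above UQ and GMC understatement (Engerix-B vs Sci-B-Vac):*

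| SD | UQ | Share above UQ | GMC understated by |
|---|---|---|---|
| 0.6 | 1,000 | 0.7% vs 5.7% | 0.3% vs 3.3% |
| 0.8 | 1,000 | 5.2% vs 22.7% | 4.0% vs 21.5% |
| 1.0 | 1,000 | 13.1% vs 40.2% | 14.0% vs 48.3% |
| 0.8 | 10,000 | 0.2% vs 2.3% | 0.1% vs 1.6% |
| 1.0 | 10,000 | 1.7% vs 10.6% | 1.4% vs 11.0% |

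**Variations.**
- *Evidence for a difference:* the z-statistic is 16.9 uncapped and 16.1 to 16.9 capped. The estimates and intervals are distorted; the evidence hardly changes.
- *600 per arm* (near the 45-and-over group): the same three intervals still exclude the uncapped ratio, with upper limits of about 4.9, 7.0 and 5.5.
- *Engerix-B SPR 0.84,* the plan's less favourable value: at UQ 1,000, 4.03 becomes 3.33 (SD 0.8) and 5.70 becomes 3.56 (SD 1.0).
- *With the LQ/2 rule also applied* (assumed LQ 5, UQ 1,000): 4.90 becomes 4.00 (SD 0.8) and 7.11 becomes 4.28 (SD 1.0).
- *Unequal spread* (assumed SDs 1.2 for Engerix-B, 0.8 for Sci-B-Vac, UQ 1,000): the ratio rises from 2.22 to 2.45 and z from 6.6 to 9.0.

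**The case against.** **Nothing in the documents fixes the size.** This stands. At an assumed UQ of 100,000 the three ratios are 3.34, 4.99 and 7.39 against 3.34, 4.99 and 7.46 uncapped, so the cap may prove immaterial. The exclusions also depend on sample size: at SD 0.8 and UQ 1,000 the capped interval reaches the uncapped ratio below about 507 per arm, a 19% loss from 626.

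**No planned conclusion changes.** This also stands. GMC is exploratory and carries no success criterion. With similar spread the bias works against the sponsor's product, and the unequal-spread example uses SDs with no source in the documents. Still, a conservative direction does not make the reported GMCs and ratios correct.

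**The cap may be the sound choice.** Protocol 3.2 promises "A validated quantitative antibody test will be used to measure anti-HBs levels in serum", but neither document says whether that validation covers manual dilution. If it does not, keeping to the initial range is defensible, so the fix is made conditional on this. The SAP may also add data rules on which the protocol is silent; the absence of the cap from the protocol is not a contradiction.

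**Readers could see the ceiling.** In part. Immunogenicity "data will be listed by subject including actual sampling times relative to dosing", so affected samples can be counted. Where the cap binds, the tabulated maximum is UQ, though not labelled as such, and the individual plots would show values stacked there. None of this corrects the GMCs, ratios or intervals, and no summary table counts the affected values.

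**Conclusion.** The concern holds. Under SAP 6.1.1 the unadjusted GMC of any arm with results above UQ is understated by construction, and the ANCOVA-adjusted GMC is expected to be. The size ranges from nil to large and depends on the unstated UQ and SD. In the equal-SD illustration the Day 196 ratio is unchanged at SD 0.6 with UQ 10,000 and falls from 7.46 to 4.49 at SD 1.0 with UQ 1,000.

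The illustration is rough. The planning SPRs apply to subjects aged 45 and over; non-responders may form a separate group; the ANCOVA covariates are ignored; and Days 28, 56, 168 and 336 were not modelled.

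The co-primary and secondary SPR analyses are unaffected if UQ is at least 10 mIU/mL. The 5.0 to <12.0 mIU/mL re-test band in SAP 6.1.1 implies that it is. The proportion reaching 100 mIU/mL is unaffected if UQ is at least 100. This is a defect in exploratory estimation that is cheap to correct before database lock, not a threat to the trial's main conclusions.

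**What to change.** Amend SAP 6.1.1 and 6.3.13.4:

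1. If the manual dilution step is confirmed as validated, use the diluted results as the analysis values for GMC, ANCOVA and descriptive summaries, and keep the capped analysis as a sensitivity analysis.
2. If validation is not confirmed, keep the capped analysis as the main one and add a sensitivity analysis using the diluted values or a censored-normal model on log10 titre.
3. In either case, treat any result above UQ without a usable diluted value as right-censored at UQ.
4. In either case, add a table giving UQ and the number of values above it by arm and visit.

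The cost is a few SAP sentences, one sensitivity analysis, one table and a check of the dilution validation. Re-testing is already planned, so no new samples or assays are needed. A protocol amendment should not be necessary, because the cap is not in the protocol's GMC method and Protocol section 9 handles changes to exploratory analyses through the study report. The downside is slightly more assay variability in the diluted values.
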